8.0 CRITERIA FOR REMOVAL FROM PROTOCOL THERAPY AND OFF STUDY CRITERIA

8.1 Criteria for Removal From Protocol Therapy

- a) Progressive disease.
- b) Adverse Events requiring removal from protocol therapy, as stated in [Section 5.0](#).
- c) Patients who receive concurrent anticancer or investigational therapy, as stated in [Section 4.1.4](#).
- d) Refusal of further protocol therapy by patient/parent/guardian.
- e) Completion of 12 cycles of therapy.
- f) Physician determines it is in patient's best interest.
- g) Non-compliance that in the opinion of the investigator does not allow for ongoing participation.
- h) Patients who develop a second malignant neoplasm.

Patients who are removed from protocol therapy (except for 8.1.g) are to be followed until they meet the criteria for Off Study (see below). Follow-up data will be required unless consent was withdrawn.

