8.2 Off Study Criteria

- a) Death.
- b) Lost to follow-up.
- c) Entry into another COG study with tumor therapeutic intent (e.g., at recurrence).
- d) Withdrawal of consent for any further data submission.
- e) The fifth anniversary of the date the patient was enrolled on this study.
- f) Patient did not receive protocol treatment after study enrollment

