9.3 Methods of Analysis

Response criteria are described in [Appendix III](#). A responder is defined as a patient who achieves a best response (as defined in [Section 10.2](#)) of PR or CR on the study prior to having an overall response of PD (as defined in [Section 10.2](#)); all others will be considered non-responders. The evaluation period for determination of the best response will be 12 treatment cycles. Response rates will be calculated as the percent of evaluable patients who are responders, and confidence intervals will be constructed accounting for the two-stage design.

Duration of response (Aim 1.2.5) will be defined as the time from first occurrence of PR or CR until the first occurrence of PD, death, or going off study. Patients who progress will be considered to have had an event, patients who die prior to progressing will be considered to have a competing event, and patients who go off study prior to progressing will be censored at time of last contact. The analysis will be done using the method of Gray.⁴⁵

Toxicity tables will be constructed to summarize the observed incidence by type of toxicity and grade. A patient will be counted only once for a given toxicity for the worst grade of that toxicity reported for that patient. Toxicity information recorded will include the type, severity, time of onset, time of resolution, and the probable association with the study regimen.

The analytic unit for monitoring for protocol-specific toxicities will be the patient-course: Each course where the patient receives the agent and either 1) has a protocol-specific toxicity event, or 2) receives at least 85% of their assigned dose during the cycle will be considered in the analysis. If there is strong evidence (posterior probability of at least 70% with at least 2 observed toxicities) that there is a per course protocol-specific toxicity probability of more than 20%, such information will be presented to the DSMC.

We will use a Bayesian rule to monitor for protocol-specific toxicities. We will assume a beta prior distribution with $\alpha = 0.52$ and $\beta = 2.08$. At least once per month, we will calculate the posterior probability (given the data) that the probability of protocol-specific toxicity exceeds the 20% threshold:

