9.4 Evaluability for Response

Any patient who is enrolled and receives at least one dose of trametinib will be considered evaluable for response.

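### Section 8.1 contradicts itself and Section 8.2 on follow-up of patients removed for non-compliance, and Section 9.3 has no censoring rule for them

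*Combined protocol and SAP*

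**What the plan says.** Section 8.1 gives eight reasons (a to h) for stopping protocol therapy. Reason g is "Non-compliance that in the opinion of the investigator does not allow for ongoing participation". The list is followed by this instruction: "Patients who are removed from protocol therapy (except for 8.1.g) are to be followed until they meet the criteria for Off Study (see below". No other reason is excepted. The sentence directly after it reads "Follow-up data will be required unless consent was withdrawn" and makes no exception for g.

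Section 8.2 gives six Off Study criteria (a to f). Non-compliance is not one of them. Three matter here: loss to follow-up (8.2.b), "Withdrawal of consent for any further data submission" (8.2.d) and "The fifth anniversary of the date the patient was enrolled on this study" (8.2.e).

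Section 9.3 defines duration of response (Aim 1.2.5) as "the time from first occurrence of PR or CR until the first occurrence of PD, death, or going off study". Progression is the event, death before progression is a competing event, and "patients who go off study prior to progressing will be censored at time of last contact".

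Section 7.1 expects follow-up data on the case report form schedule, again without excepting g.

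**The concern.** A patient removed under 8.1.g who has not withdrawn consent is still on study by Section 8.2, but is outside the instruction to be followed. One sentence of Section 8.1 releases the site from following the patient, and the next requires follow-up data. Sites have to choose.

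The choice bears on duration of response. That analysis needs the date of progression and, because death is a competing event, the date of any death before progression. If an 8.1.g responder is not followed, either may go unrecorded. The loss may be informative: trametinib is taken daily for up to 12 cycles, and missed doses could reflect intolerance or lack of benefit. The label is also the investigator's opinion, given in an open-label trial with response and tolerability already known. With few responders expected, one such patient counts.

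**Working it through.** **1. The provisions side by side, for an 8.1.g patient who has not withdrawn consent**

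| Place | What follows for this patient |
|---|---|
| 8.1, instruction after the list | Not covered by follow-up until Off Study |
| 8.1, next sentence | Follow-up data required |
| 7.1, note on follow-up | Data expected on the form schedule |
| 8.2 | Still on study; no criterion is met by non-compliance |
| 9.3 | No censoring rule; the rule given is for patients who go off study |

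The first row conflicts with the second and third. The fourth and fifth show that the exception leads to a status that the analysis section does not handle.

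**2. Does it touch the primary design?** The inputs are from Section 9.2: 10 + 10 patients, stop at 0 of 10, declare effective at 3 or more of 20, response rates 5% and 25%.

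- Early stopping at 5%: 0.95^10 = 0.5987 (stated 0.599).
- Expected sample size at 5%: 10 + 10 × (1 − 0.5987) = 14.01 (stated 14.01).
- Probability of declaring the agent effective: the sum over x = 1 to 10 of P(X1 = x) × P(X2 ≥ max(0, 3 − x)), with X1 and X2 binomial(10, p). This gives 0.0686 at 5% (stated 0.069) and 0.8820 at 25% (stated 0.882).

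The plan's figures are reproduced, and none depends on follow-up after therapy. Section 9.4 also keeps these patients in the denominator: "Any patient who is enrolled and receives at least one dose of trametinib will be considered evaluable for response".

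**3. Size for duration of response**

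- Expected responders at the 25% rate: 20 × 0.25 = 5. One affected responder is 1/5 = 20% of the set. With 3 responders, the fewest that can lead to a positive conclusion, it is 1/3 = 33%.
- The documents give no rate of removal under 8.1.g. Let q be that rate, assumed equal and independent across patients. The expected number of removals among 20 is 20q, and the chance that at least one of k responders is affected is 1 − (1 − q)^k.

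| Assumed q | Expected removals of 20 | At least 1 of 5 responders | At least 1 of 3 responders |
|---|---|---|---|
| 2% | 0.4 | 9.6% | 5.9% |
| 5% | 1.0 | 22.6% | 14.3% |
| 10% | 2.0 | 41.0% | 27.1% |
| 15% | 3.0 | 55.6% | 38.6% |

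**4. What is still captured.** Section 11.3.1 keeps serious adverse events more than 30 days after the last dose reportable when at least possibly related. Sections 11.3.3 and 11.7 do the same for late deaths, and require reports of all deaths within 30 days. None excepts 8.1.g. A death after 30 days that is judged unrelated needs no expedited report (11.3.3), yet in a responder who has not progressed it is a competing event under 9.3. That death and the progression date are what could be missed.

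**The case against.** The strongest reply is that this is a wording slip with little behind it. The sentence requiring follow-up data, and the note in Section 7.1, already cover 8.1.g patients; safety reporting continues; the primary endpoint is untouched; and patients too non-compliant to remain on therapy may be hard to follow anyway. Much of this stands, and it limits the point to a minor one. It does not remove the contradiction. One could read the second sentence of 8.1 as applying only to the patients named in the first, but it does not say so. Even on that reading, 8.2 leaves the patient on study and 9.3 has no rule. Patients who cannot be reached are already provided for by 8.2.b.

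A reader might infer more than the documents support:

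- *That 8.1.g patients are exempt from all follow-up.* The next sentence of 8.1 says otherwise; the text conflicts rather than clearly exempting them.
- *That their late toxicity is lost.* Related late serious adverse events and deaths remain reportable for everyone.
- *That such responders are censored at removal.* Section 9.3 does not say this. Its rule uses last contact and applies to patients who go off study, which these patients have not done.
- *That at least about 49 months of follow-up are given up per patient.* Five years less twelve 28-day cycles is 1,826 − 336 = 1,490 days, about 49 months. But the next cycle may start up to 14 days after the last one ends (Sections 4.2.3, 4.3.3 and 4.4.3). Eleven such gaps leave 1,490 − 154 = 1,336 days, about 44 months. Death or entry into another therapeutic study of the group (8.2.a, 8.2.c) can end follow-up sooner, so there is no floor.

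That sites would move patients between refusal (8.1.d), physician decision (8.1.f) and non-compliance (8.1.g) is possible, but nothing in the documents shows it.

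**Conclusion.** Wrong as written: an internal contradiction, minor, affecting secondary aims only. Section 8.1 conflicts with its own next sentence and does not fit Section 8.2, and Section 9.3 does not say how to treat a patient who is on study but not followed.

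The consequence falls mainly on duration of response, and only if a site applies the exception to a patient who had already responded. One such patient would be about 20% of an expected 5 responders; the chance of at least one is about 10% to 56%. This rests on the design's 25% response rate, full enrollment of 20 evaluable patients, and assumed non-compliance rates of 2% to 15%. Whether the loss is informative, and in which direction, cannot be settled from the documents. If under-dosing makes progression more likely, missed progressions would make responses look longer than they are.

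**What to change.** Delete the parenthetical exception for 8.1.g in Section 8.1, so that every patient removed from protocol therapy is followed until a Section 8.2 criterion is met. That aligns the two sentences of 8.1 with each other and with 8.2, and leaves the censoring rule in 9.3 sufficient as it stands. If the letter g is a mistaken cross-reference, which the documents do not settle, the text needs correcting all the same.

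The cost is a few extra follow-up contacts, in patients who may be hard to reach. Section 8.2.b covers those who cannot be reached, and 8.2.d covers families who withdraw consent to data submission. The sample size, decision rule and treatment do not change.

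The alternative is to list non-compliance in 8.2 and to state its censoring, with a sensitivity analysis, in 9.3. That would also make the sections agree, but it accepts a loss of data that deletion avoids.

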8.2 Off Study Criteria

- a) Death.
- b) Lost to follow-up.
- c) Entry into another COG study with tumor therapeutic intent (e.g., at recurrence).
- d) Withdrawal of consent for any further data submission.
- e) The fifth anniversary of the date the patient was enrolled on this study.
- f) Patient did not receive protocol treatment after study enrollment

9.0 STATISTICAL CONSIDERATIONS

9.1 Sample Size and Study Duration

COG study AAML0122 (for newly diagnosed JMML) accrued at an average annual rate of 15 patients/year in the US. Assuming roughly half of these newly-diagnosed patients relapse or are refractory to chemotherapy, we can expect an accrual rate of 7.5 relapsed/refractory patients/year. With these entry rates, the probability of accruing 10 patients to complete the initial stage of evaluation within 20 months is 80% and within 24.5 months is 90%. The corresponding probability for enrolling 20 patients in 38 months is 80% and within 43 months is 90%. Allowing for a 20% inevaluability rate, a minimum of 10 patients and a maximum of 24 patients are anticipated. The study will likely require 2.5 to 3.5 years for sufficient patient enrollments to evaluate trametinib in relapsed/refractory JMML.

9.2 Study Design

The primary endpoint will be objective response by the criteria listed in [Section 10.2](#). The following Simon two-stage design will be used.

	Cumulative Number of Responses	Decision
Stage 1: Enter 10 patients	0	Terminate the trial: agent ineffective
	1 or more	Inconclusive result, continue trial (proceed to Stage 2)
Stage 2: Enter 10 additional patients	2 or less	Terminate the trial: agent ineffective
	3 or more	Terminate the trial: agent effective

We will consider trametinib not of sufficient interest for further evaluation in a disease category if the true response rate is 5% and of sufficient interest if the true response rate is 25%. If the agent has a true response rate of 5%, the rule described above will identify it of sufficient interest for further study with probability 0.069 (type I error), and the trial will have an expected sample size of 14.01 with 59.9% probability of early termination.

If the agent has a true response rate of 25%, the rule described above will identify it of sufficient interest for further study with probability 0.882 (power against the alternative hypothesis $p = 0.25$). An expanded table of possible true response rates is below:

True response rate	Probability of stopping early for lack of activity	Probability of identifying agent as effective	Expected number of patients accrued
5%	0.599	0.069	14.01
10%	0.349	0.299	16.51
15%	0.197	0.560	18.03
20%	0.107	0.759	18.93
25%	0.056	0.882	19.44
30%	0.028	0.947	19.72
35%	0.013	0.978	19.87

9.3 Methods of Analysis

Response criteria are described in [Appendix III](#). A responder is defined as a patient who achieves a best response (as defined in [Section 10.2](#)) of PR or CR on the study prior to having an overall response of PD (as defined in [Section 10.2](#)); all others will be considered non-responders. The evaluation period for determination of the best response will be 12 treatment cycles. Response rates will be calculated as the percent of evaluable patients who are responders, and confidence intervals will be constructed accounting for the two-stage design.

Duration of response (Aim 1.2.5) will be defined as the time from first occurrence of PR or CR until the first occurrence of PD, death, or going off study. Patients who progress will be considered to have had an event, patients who die prior to progressing will be considered to have a competing event, and patients who go off study prior to progressing will be censored at time of last contact. The analysis will be done using the method of Gray.⁴⁵

Toxicity tables will be constructed to summarize the observed incidence by type of toxicity and grade. A patient will be counted only once for a given toxicity for the worst grade of that toxicity reported for that patient. Toxicity information recorded will include the type, severity, time of onset, time of resolution, and the probable association with the study regimen.

The analytic unit for monitoring for protocol-specific toxicities will be the patient-course: Each course where the patient receives the agent and either 1) has a protocol-specific toxicity event, or 2) receives at least 85% of their assigned dose during the cycle will be considered in the analysis. If there is strong evidence (posterior probability of at least 70% with at least 2 observed toxicities) that there is a per course protocol-specific toxicity probability of more than 20%, such information will be presented to the DSMC.

We will use a Bayesian rule to monitor for protocol-specific toxicities. We will assume a beta prior distribution with $\alpha = 0.52$ and $\beta = 2.08$. At least once per month, we will calculate the posterior probability (given the data) that the probability of protocol-specific toxicity exceeds the 20% threshold:

$$P(p_{\text{protocol-specific toxicities}} > 20\% | \text{Data}) = \frac{\int_{0.2}^1 \binom{n}{x} p^x (1-p)^{n-x} \cdot \frac{\Gamma(2.6)}{\Gamma(0.52)\Gamma(2.08)} \cdot p^{-0.48} (1-p)^{1.08} dp}{\int_0^1 \binom{n}{x} q^x (1-q)^{n-x} \cdot \frac{\Gamma(2.6)}{\Gamma(0.52)\Gamma(2.08)} \cdot q^{-0.48} (1-q)^{1.08} dq}$$

Here n is the number of protocol-specific toxicity-evaluable cycles and x is the number of such cycles on which a protocol-specific toxicity event is observed. Examples of situations in which this rule will indicate protocol-specific toxicities have been noted and are presented below:

Number of failures	Number of patient-cycles
2	6
3	10
4	14
5	19
6	23
7	28
8	32
9	37
10	41
11	46
12	51
13	55
14	60

Protocol-specific toxicities of interest include rash, diarrhea, ejection fraction changes, hypertension, prolonged QTc, pneumonitis, visual changes, ALT increase, AST increase, and bilirubin increase.

If there is strong evidence (posterior probability of at least 70% with at least 2 observed toxicities) that there is a per course protocol-specific toxicity probability of more than 20%, such information will be presented to the DSMC.

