APPENDIX III: RESPONSE CRITERIA FOR PATIENTS WITH JMML

Table 1: Variables for evaluation of response to therapy in JMML

Variables for Response	Definition of response			Definition of disease progression or relapse (applicable to all patients)	
	Assessment of CR and PR is feasible if the following are present before therapy	Requirement for CR for each variable (vCR)	Requirement for PR for each variable (vPR)	Requirement for PD for each variable (vPD)	
Clinical variables	1) WBC count	>20 × 10 ⁹ /L	3.0 – 15.0 × 10 ⁹ /L	Decreased by ≥50% over pretreatment but still >15 × 10 ⁹ /L	Increase by ≥50% and ≥20 × 10 ⁹ /L
	2) Myeloid and erythroid precursors and blasts in PB*	≥ 5%	0-1%	Decreased by ≥50% over pretreatment but still ≥ 2%	Increase from the baseline: < 5%: ≥ 50% increase and ≥ 5% ≥ 5%: ≥ 50% increase of total % of myeloid and erythroid precursors and blasts
	3) Platelet count	<100 × 10 ⁹ /L	>100 × 10 ⁹ /L	For patients starting with ≥ 20 × 10 ⁹ /L platelets: absolute increase of ≥ 30 × 10 ⁹ /L For patients starting with < 20 × 10 ⁹ /L platelets: increase by ≥ 100% and > 20 × 10 ⁹ /L	Development of transfusion dependency or if patients have the baseline of the platelet count of ≥30 × 10 ⁹ /L, decrease by ≥50% and <100 × 10 ⁹ /L
	4) BM blasts	≥5%	<5%	Decreased by ≥50% over pretreatment but still ≥5%	Increase from base line; < 5%: ≥ 50% increase and ≥ 5% ≥ 5%: ≥ 50% increase of BM blasts
	5) Spleen size				
	a) Clinical evaluation or	≥2 cm under the costal margin	No splenomegaly	50% decrease by cm under the costal margin	Increase by ≥100% if baseline <4cm from under the costa margin ≥50% if baseline 5-10cm >30% if baseline >10 cm
b) Sonography	Length of spleen ≥ 150% of upper limit of normal range	No splenomegaly	>25% decrease by length, but still splenomegaly	Increase by ≥25% of length	
6) Extramedullary disease#	Extramedullary leukemic infiltration	No evidence of extramedullary leukemic infiltration in any organ	-	Worsening or new lesions of extramedullary leukemic infiltration	
7) Cytogenetic response	Somatic cytogenetic abnormality detected	Normal karyotype	-	Reappearance or additional acquirement of cytogenetic abnormalities	
8) Molecular response	Somatic genetic anomalies detected**	Absence of somatic genetic anomalies	-	Reappearance or additional acquirement of JMML-specific somatic gene abnormalities	

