9) Chimerism response (only for patients after HSCT)	>15% autologous cells after allo-HSCT	Complete donor chimerism	-	50% increase and >5% increase of autologous cells and >5%	

CR: complete response, PR: partial response, PD: progressive disease, WBC: white blood cell, PB: peripheral blood, BM: bone marrow

*Myeloid precursors include promyelocytes, myelocytes, and metamyelocytes. The myeloid and erythroid precursors and blasts in PB are given as % of the total nucleated cells in PB (WBC including erythroblasts).

**in *NF-1*, *PTPN11*, *NRAS*, *KRAS*, *RRAS2*, or *CBL*, thus the mutation are thought to be initiating. In patients with germ-line *NF-1*, *PTPN11* or *CBL* mutation, only acquired mutations can be evaluated for response and relapse after therapy. The germ-line mutation remains even if patients achieved complete molecular response. The molecular response will be determined using the “JMML Mutant Allele Burden” assay.

Criteria for progression including WBC, platelet count and spleen size cannot be used in the setting of an active infection.

#Extramedullary disease includes infiltration of skin, lung, and very rarely cranial nerves or central nervous system.

Table 2: Definition of response following therapy other than HSCT in JMML

Clinical remission status: parameter 1-6 of table 1		Genetic remission status: parameter 7-9 of table 1	
Clinical complete remission (cCR)	Patient fulfills the criteria of CR of all applicable clinical variables 1-6 of table 1 The response parameters must be maintained for at least 4 weeks.	Genetic complete remission (gCR)	Defined if the patient shows a normal karyotype and absence of acquired mutations in PTPN11 , NF-1 , NRAS , KRAS , or CBL .
Clinical partial remission (cPR)	Defined if the patient does not fulfill the criteria of cCR, but vPR was achieved in at least one of clinical variables (1 – 6) and none of clinical variables showed vPD.	-	-
Clinical stable disease (cSD)	Defined if the patient does not fulfill the criteria of cCR and cPR, but none of the parameter showed vPD.	Genetic stable disease (gSD)	Defined if the patient does not fulfill the criteria of gCR, but none of the genetic parameters (7-9) showed vPD.
Clinical progressive disease (cPD)	Defined if any of the parameters 1-6 showed vPD.	Genetic progressive disease (gPD)	Defined if any of the parameters 7-9 showed vPD.

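### As written, duration of response runs on through transplant or other new therapy started before progression; Section 9.3 neither says this is intended nor reports that time separately

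*Combined protocol and SAP*

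**What the plan says.** Section 9.3 of the combined protocol and SAP defines duration of response as "the time from first occurrence of PR or CR until the first occurrence of PD, death, or going off study". Progression (PD) is the event, death before PD is a competing event, and "patients who go off study prior to progressing will be censored at time of last contact". The analysis uses Gray's competing-risk method. Transplant (HSCT) and other new therapy are not named as an event, a competing event or a reason to censor.

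Section 8.1 lists the reasons for stopping protocol therapy. They include completing 12 cycles (8.1.e) and the physician's view of the patient's interest (8.1.f). It then says: "Patients who are removed from protocol therapy (except for 8.1.g) are to be followed until they meet the criteria for Off Study".

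Section 8.2 lists what ends study participation: death, loss to follow-up, entry into another COG therapeutic study (8.2.c), withdrawal of consent for further data, "The fifth anniversary of the date the patient was enrolled on this study", and never having received protocol treatment. Transplant or other therapy given outside a COG study is not on the list.

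**The concern.** Duration of response to a single agent is normally read as how long that agent's effect lasts. Under these three sections the clock does not stop when a responder moves to transplant or other anti-leukemia therapy without having progressed. A long remission after transplant lengthens the reported duration, and a relapse after transplant enters as a PD event. Either way the result combines what trametinib did with what the next treatment did, and Section 9.3 plans no output that separates them.

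The situation is foreseeable, though the documents do not say how common it will be. Section 3.2.3.1 admits patients after one cycle of intensive frontline therapy or two cycles of a demethylating agent, so a patient may enrol without a prior transplant. Trametinib stops after 12 cycles while follow-up continues to five years. With few responders, one or two such patients could shape the whole result.

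**Working it through.** **Plan's own figures.** The documents give no figure for duration of response. The nearest is the Simon design in Section 9.2, which sets the number of responders. At a true rate of 25%, early stopping has probability 0.75^10 = 0.056 and the expected sample is 10 + 10 × (1 − 0.0563) = 19.44, both as printed. Expected responders are 0.25 × 19.44 = 4.86, or about 5. One or two of five is 20% to 40% of the data for this aim.

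**Length of the window.** Twelve 28-day cycles are 336 days, or 11.0 months. Five years is 60.0 months. Up to 60.0 − 11.0 = 49 months after trametinib can count, less if cycles are delayed.

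**Illustration.** These inputs are assumptions:
- Exponential times, with median time to PD on or after trametinib alone of 9 months (also 6 and 24).
- A share f of 15%, 30% or 60% of responders transplanted before PD. This is a lifetime share, not a 24-month share.
- Half relapse after HSCT (r = 0.5), with mean time m = 8 months. Section 2.1 says about half relapse but gives no time horizon; the 8 months has no source in the documents.
- No transplant death. Horizon T = 24 months from response.

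Formulas:
- PD hazard l = ln 2 / median; transplant hazard h = l·f/(1 − f); s = l + h.
- Counted time before HSCT = (1 − e^(−sT))/s.
- Counted time after HSCT = ∫ from 0 to T of h·e^(−su)·[(1 − r)(T − u) + r·m·(1 − e^(−(T−u)/m))] du.
- PD with new therapy competing = (l/s)(1 − e^(−sT)); new therapy = (h/s)(1 − e^(−sT)).
- PD as written = the competing-event PD figure + h·r·∫ from 0 to T of e^(−su)(1 − e^(−(T−u)/m)) du.
- PD if censored at new therapy = 1 − e^(−lT), provided the timing of new therapy is unrelated to PD risk.

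For median 9 and f = 30%: l = 0.0770, h = 0.0330, s = 0.1100. Time before HSCT is (1 − e^(−2.64))/0.1100 = 8.44 months and time after is 3.26 months, so the share after is 3.26/11.70 = 28%.

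| f (median 9) | Months before | Months after | Share after | PD as written | PD if censored | PD, competing | New therapy, competing |
|---|---|---|---|---|---|---|---|
| 15% | 9.78 | 1.50 | 13% | 81% | 84% | 75% | 13% |
| 30% | 8.44 | 3.26 | 28% | 77% | 84% | 65% | 28% |
| 60% | 5.14 | 7.76 | 60% | 66% | 84% | 40% | 59% |

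The share after HSCT for the same three values of f is 20%, 39% and 71% with a 6-month median, and 5%, 11% and 32% with a 24-month median. Part of that fall comes from the model: h is tied to l, so longer responses are transplanted later. At a 24-month median only 8%, 19% and 49% are transplanted by month 24.

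Allowing 20% transplant death at a mean of 4 months lowers the central share from 28% to 23%.

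The chance that at least one of five responders is transplanted before PD is 1 − (1 − f)^5 = 56%, 83% or 99%.

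**The case against.** The strongest reply is that a rule exists. Sections 9.3, 8.1 and 8.2 together classify every responder, and following patients regardless of later therapy is a recognised estimand. That stands: a reader might infer that the plan has no rule, and the documents do not support it. What is missing is a statement that follow-through is intended and a report that separates the periods.

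The case report forms are posted elsewhere, so the start date of new therapy may already be collected. That also stands. The gap is in the planned analysis, not necessarily in the data.

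The illustration rests on inputs the documents do not supply, and its results run from 5% to 71%. This stands, and it is why the size is called unknown. Section 3.2.3.1 also counts transplant conditioning as frontline therapy, so some patients will enrol already transplanted.

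Three stronger readings should be set aside:
- **Transplant scored as progression.** Platelet progression in Appendix III includes "Development of transfusion dependency or if patients have the baseline of the platelet count" (a further condition follows), and the only stated exclusion is "Criteria for progression including WBC, platelet count and spleen size cannot be used in the setting of an active infection". A reader might infer that transfusion after conditioning makes every transplant a PD. But overall PD is built from Table 2, which is headed for therapy other than HSCT, and transfusion dependency is not the same as transfusion during recovery. The reading is strained.
- **Different handling on a COG study.** Entry under 8.2.c would censor a patient whose identical therapy elsewhere would be counted through. The documents do not show this route to be likely before PD: the criterion's own example is recurrence.
- **A bias in trametinib's favour.** PD after new therapy is counted as well as remission, so the direction is not fixed.

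It can also be said that one sentence and a listing would suffice. With about five responders the listing does carry most of the information, but the added analysis uses the planned method and costs little.

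**Conclusion.** The point holds in limited form, as an optional improvement. The reading of the text is secure: outside a COG study, a responder who starts new therapy before PD stays at risk until PD, death, five years from enrolment or another off-study event, and that time is reported as duration of response to trametinib.

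The consequence is less certain, because no transplant rate is given. At the central assumptions (9-month median, 30% transplanted), about 28% of the counted time in the first 24 months follows transplant. The 24-month PD figure is then 77% as written, 84% if censored at new therapy, and 65% with new therapy as a competing event. These are three different estimands; the gaps between them do not measure a bias.

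Only secondary Aim 1.2.5 is affected, and it carries no hypothesis test or decision rule. New therapy after a response does not change whether the patient responded, so the primary endpoint and the Simon decision stand.

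**What to change.** In Section 9.3:
1. If follow-through is kept, say so: responders are followed for PD and death regardless of later therapy.
2. Add an analysis by the cumulative-incidence method already planned, in which HSCT or any other anti-leukemia therapy started before PD is a competing event alongside death. Apply it the same way on or off a COG study.
3. Add a patient-level listing of responders with dates of response, last trametinib dose, new therapy, PD and death.

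Which analysis is the main one is for the sponsor to name before results are known.

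The cost is a few sentences, a little more analysis and possibly one more data field (date of first subsequent therapy) if the forms do not already have it. The added analysis will contain fewer PD events. Sample size and design do not change.
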